5. STUDY POPULATION

5.1. General

The enrolled analysis set will be used for all study population summaries unless otherwise noted. Summaries will be presented by cohort and overall, as appropriate.

5.2. Patient Disposition

Data from patients screened and screened but not enrolled (with reason for no enrollment) will be summarized overall using patient counts only. Participants who were enrolled in Period 1, patients who continued to Period 2, patients who are randomized in Period 3, patients randomized but not treated in Period 3, pharmacokinetic, pharmacogenomics and safety analysis sets, treatment completers (patients who have completed the procedures and assessments required in period 3, i.e 28 days after TV44749 administration), patients who complete the trial (patients who have completed the procedures and assessments required through treatment and follow-up period), patients who withdraw from the study, patients who discontinue the trial prior to TV44749 formulation administration, patients who discontinue the trial during Period 3 (day R1 to day R29) and patients who discontinue the trial during the Follow-up period (day R30 to day R84) will be summarized using descriptive statistics. Data from patients who withdraw from the study will also be summarized by reason for withdrawal using descriptive statistics. The summary will be based on all patients.

5.3. Demographics and Baseline Characteristics

The continuous variables of patient age, weight, height, and body mass index (BMI) will be summarized using descriptive statistics. The categorical variables of patient sex, race, ethnicity, and smoking status will be summarized using descriptive statistics for each category. Missing categories will be presented if necessary.

5.4. Medical History

All medical history will be coded using the Medical Dictionary for Regulatory Activities (MedDRA). The incidence of medical history abnormalities will be summarized using descriptive statistics by system organ class (SOC) and preferred term. Patients are counted only once in each preferred term and SOC category. Summaries will be presented by cohort and for all patients.

5.5. Prior Therapy and Medication

Any prior therapy, medication, or procedure a patient has had within 30 days before study drug administration will be recorded on the CRF. Trade name or INN, indication, and dosage will be recorded. The sponsor will encode all therapy and medication according to the World Health Organization (WHO) drug dictionary (WHO Drug).

The incidence of prior therapies and medications will be summarized using descriptive statistics by therapeutic class and preferred term. Patients are counted only once in each therapeutic class category, and only once in each preferred term category.

5.6. *Electrocardiography*

Electrocardiogram findings (normal, abnormal not clinically significant, abnormal clinically significant, and missing) in screening period, AP WO period (day 3) and on day R1 in period 3 will be summarized using descriptive statistics.

5.7. *Childbearing Potential and Methods of Contraception*

For female patients, information related to childbearing potential, and menopause will be collected at the time points specified in Table 1 to Table 5 of the trial protocol. Data will be listed.

For female and male patients, methods of contraception will be collected at the screening period. Data will be listed.

5.8. *Trial Protocol Deviations*

Data from patients with any important protocol deviations during the trial will be summarized for overall and each category using descriptive statistics. All protocol deviations will be listed.

6. PHARMACOKINETIC ANALYSIS

6.1. General

The pharmacokinetic analysis set will be used for all plasma concentration descriptive summaries, graphs, and listings and for PK parameter listings, unless otherwise stated. The pharmacokinetic analysis set will be used for parameter descriptive summaries, graphs, and statistical analyses, unless otherwise stated. No formal inferential statistical analyses of PK data are planned.

6.2. Values below the Limit Quantification or Missing

The lower limit of quantitation (LLOQ) is 10 pg/mL for the olanzapine formulations (ZYPREXA IM or sc extended-release formulations).

For summary displays of pharmacokinetic concentration data, values below the limit of quantitation (BLQ) will be imputed as $\frac{1}{2} \times$ lower limit of quantitation (LLOQ). If the mean concentration at a timepoint is less than LLOQ, then “BLQ” will be reported in place of summary statistics. In addition, BLQ values will be treated as 0 in plasma concentration data figures (individual subject plot and mean concentration plots).

For calculating PK parameters, a BLQ value at time 0, at a sampling time before the 1st quantifiable plasma drug concentration, or at a sampling time between 2 quantifiable concentrations will be treated as 0. All other BLQ values (ie, those occurring at the end of the profile) will be treated as missing for the computation of pharmacokinetic parameters.

In data listings, the data will be reported as is (ie, no imputation).

6.3. Pharmacokinetic Concentrations

Plasma concentration data will be individually listed and summarized by nominal time point treatment and cohort using descriptive statistics (n, mean, standard deviation, geometric mean [if appropriate], geometric coefficient of variation [%coefficient of variation (CV)] [if appropriate], median, minimum, and maximum).

6.4. Graphical Summaries

Linear and semi-logarithmic plots of mean (\pm SD) plasma concentration by scheduled sampling time will be provided. Plots will show time in hours for ZYPREXA IM and time in days for olanzapine sc extended-release formulations. Plots will be presented separately for ZYPREXA IM, and for olanzapine sc extended-release formulations by cohort (including a separate plot up until day R29).

Linear and semi-logarithmic plots of the individual plasma concentration by actual sampling time will be provided by patient (one patient per page). For each patient, there will be a separate plot for ZYPREXA IM and olanzapine extended-release formulation. Plots will show time in hours for ZYPREXA IM (starting with day 4) and days for olanzapine extended-release formulations (starting with R1).

6.5. Pharmacokinetic parameters

Pharmacokinetic parameters will be calculated from individual olanzapine plasma concentrations, actual elapsed time profiles by non-compartmental methods, when possible. The PK parameters detailed in [Table 1](#) will be calculated following ZYPREXA im administration. Additional PK parameters may be calculated if deemed necessary.

Table 1: Description of Pharmacokinetic Parameters Following Zyprexa IM Administration

Pharmacokinetic Parameter	Description
C_{max}	Maximum observed plasma drug concentration (C_{max}) over the 24-hour period following single-dose administration of ZYPREXA im (day 4), obtained directly from the observed concentration time data
AUC_{0-t}	AUC following single-dose administration of ZYPREXA im to last measurable concentration (AUC_{0-t}) (pre-dose ZYPREXA im to 216 hours post im administration); calculated by lin- up log down trapezoidal method
λ_z	apparent plasma terminal elimination rate constant (λ_z), estimated by linear regression of the terminal portion of the log-concentration by time curve;
███████████	███████████
███████████	███████████
$AUC_{0-\infty}$	AUC extrapolated to infinity ($AUC_{0-\infty}$) calculated from last measurable plasma concentration following single dose administration of ZYPREXA im (pre-dose ZYPREXA im to 216 hours post im administration); calculated by linear-up log-down method
███████████	███████████
████	███████████
████	███████████
████	███████████

The PK parameters detailed in [Table 2](#) will be calculated following sc olanzapine extended -release formulation administration. Additional PK parameters for olanzapine extended -release formulation may be calculated if deemed necessary.

Table 2: Description Of Pharmacokinetic Parameters Following sc Olanzapine Extended-Release Formulation Administration

Pharmacokinetic parameters will be individually listed and summarized for each treatment and cohort (ZYPREXA im, and Olanzapine sc extended-release formulations) using descriptive statistics (n, mean, standard deviation, geometric mean [if appropriate], geometric coefficient of variation (%CV) [if appropriate], median, minimum, and maximum).

7. SAFETY ANALYSIS

7.1. General

The safety analysis set will be used for all safety analyses. Summaries will be presented by cohort and treatment (including any of the IMPs; ZYPREXA im or Olanzapine sc extended-release formulations) and overall, unless otherwise stated.

For continuous variables, descriptive statistics (n, mean, standard deviation, standard error [SE], median, minimum, and maximum) will be provided for actual values and changes from baseline to each time point. For categorical variables, participant counts and percentages will be provided.

7.2. Adverse Events

Adverse events will be collected and recorded from the time a patient signs the informed consent to the end of follow-up period (day R84).

All adverse events will be coded using the Medical Dictionary for Regulatory Activities (MedDRA). Summaries will be presented for all adverse events occurring after the first dose of IMP (ZYPREXA im and/or Olanzapine extended-released formulation), as overall and by Common Terminology Criteria for Adverse Events [CTCAE] grade, including AEs determined by the investigator to be related to IMP and/or medical device (defined as related or with missing relationship), serious adverse events and injection site adverse events. Adverse events missing relationship to study drug will be included in the study drug related summary. A summary of occurrence of adverse events, serious adverse events and injection site adverse events will be presented separately for period 1 + 2 (from the administration timepoint of Zyprexa IM until and not including the administration timepoint of Olanzapine extended-release formulation), for period 3 (day R1 to day R29) and for the follow up period (day R30 to day R84). The occurrence of adverse events, serious adverse events and injection site adverse events will also be listed for the Wash-Out period (from day 1 to the administration of Zyprexa im). The incidence of adverse events will be summarized using descriptive statistics by SOC and PT. For the incidence of adverse events, patients are counted only once in each SOC category, and only once in each PT category. For the summary by grade, patients are counted at the worst grade.

Protocol defined adverse event of special interest (PDAESI) (section 8.4.8 of the study protocol) will also be summarized and presented by cohort separately for period 1 + 2 (from the administration timepoint of Zyprexa IM until and not including the administration timepoint of Olanzapine extended-release formulation), for period 3 (day R1 to day R29) and for the follow-up period (day R30 to day R84). PDAESI that required reporting to Sponsor's Global PV for evaluation may be presented in a separate summary table.

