
To evaluate the safety and tolerability following a single-dose of immediate-release ZYPREXA im in participants with schizophrenia or schizoaffective disorder.
	
The safety and tolerability measures/parameters are:
 
 • Occurrence of adverse events during the 24-hour period following administration of ZYPREXA im (day 4 to day 5) • Change in clinical laboratory (chemistry, hematology) tests, vital sign measurements (body temperature, respiratory rate, pulse rate, and blood pressure) during the 24-hour period following administration of ZYPREXA im (day 4 to day 5) • ECG findings during the 24-hour period following administration of ZYPREXA im (day 4 to day 5) • Use of concomitant medication during the 24-hour period following administration of ZYPREXA im (day 4 to day 5) • Discontinuation for any reason during the 24-hour period following administration of ZYPREXA im (day 4 to day 5) • Discontinuation due to an adverse event during the 24-hour period following administration of ZYPREXA im (day 4 to day 5) • Local tolerability and pain during the 24-hour period following administration of ZYPREXA im (day 4 to day 5) 
[REDACTED]
 
[REDACTED]
 
[REDACTED]

To evaluate the overall safety of the trial in participants with schizophrenia or schizoaffective disorder.
	
The safety measures/parameters are:
 
 • Occurrence of adverse events during trial participation (screening to day R84) • Use of concomitant medication during trial participation (screening to day R84) • Discontinuation for any reason from enrollment until end of trial (day 1 to day R84) • Discontinuation due to an adverse event from enrollment until end of trial (day 1 to day R84) 
[REDACTED]

Statistical Analysis Plan

Pharmacokinetic Trial – Schizophrenia Participants Trial TV44749-NPC-10205

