The screening period of up to 40 days in duration will be performed in an outpatient setting. Participants who meet screening eligibility criteria will be enrolled and undergo an inpatient WO of 3 days from their current antipsychotic treatment. Thereafter, participants will remain in the clinical unit (CU) and will continue to period 1 (day 4) that will include a single injection of 5 mg of ZYPREXA im, immediate-release solution, administered to the gluteal muscle. Prior to the im injection, participants' eligibility will be reconfirmed (Table 1 of the trial protocol). Subsequently, participants will continue to the follow-up period 2 (day 5 to day 12). The first 3 days of period 2 will be performed in an inpatient setting. Participants will be discharged on day 7. The remaining visits of period 2 (day 8 and day 9) may be performed in an inpatient or an outpatient setting per Investigator's discretion and participants' preference. Participants will be readmitted to the CU on day 12 (Table 2 of the trial protocol), which is a mandatory visit for all patients. Period 2 may be extended up to 7 days maximum, post Visit 10 (Visit 10 counts as day 1, so day 7 is R1, at maximum) for all cohorts per Principal Investigator and Sponsor discretion. In the event of extension of period 2, participants will return to the clinic on day 13 (Visit 11) for an unscheduled visit to collect the 216 h PK sample; if this extension is not required, participants will skip Visit 11 and proceed to Visit 12. For those who proceed directly to period 3, the 216 h post-dose sample will be collected prior to sc dosing as shown in Table 3 of the trial protocol for cohort 1A and Table 4 of the trial protocol for cohorts 1B, 2, and 3. During period 2, participants will resume treatment with the allowed antipsychotic treatments and discontinue 24 h prior to sc injection on day R1.

Thereafter, on day R1, participants will enter treatment period 3 (day R1 to day R29). During this period participants will discontinue treatment with any of the allowed antipsychotics they were receiving during period 2. On day R1 of this period, participants will be assigned to 1 of the 3 single-dose cohorts and will be administered 1 of 3 olanzapine extended-release sc formulations (TV-44749) in the abdomen. Period 3 includes both an inpatient and an outpatient period.

During period 3, participants will be treated with 1 of the following olanzapine extended-release (TV-44749) formulations:

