7.6.1. Overall Tolerability

Overall tolerability will be assessed after all participants have completed the final assessments and will be based upon the number (%) of participants who failed to complete the trial and the number (%) participants who failed to complete the trial due to AEs will be provided. A summary will be provided as part of the AEs and disposition summaries, separately for period 1+2 up until the Olanzapine extended-release formulation administration, for period 3 (day R1 to day R29), and for the Follow-up period (day R30 to day R84).

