7.11. Concomitant Medications or Therapies

Concomitant therapies and medications, including medications that are taken on an as needed basis and occasional therapies, will be monitored during the study. All concomitant medications will be coded using the WHO Drug.

The incidence of concomitant medications and therapies will be summarized using descriptive statistics by therapeutic class category and PT. Patients are counted only once in each therapeutic class, and only once in each PT category. A separate summary will be provided for the screening period, for period 1 and period 2 (day 4 up until day R1), for period 3 (day R1 to day R29) and for the Follow-up period (day R29 to day 84).

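### SAP Section 7 does not deliver three sets of descriptive safety measures as SAP Section 1 defines them: the 24-hour im measures, the period 3 QTcF cut-offs, and the day R29 boundary

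*SAP*

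**What the plan says.** **24-hour im measures.** SAP Section 1.4 lists "Occurrence of adverse events during the 24-hour period following administration of ZYPREXA im (day 4 to day 5") among the exploratory measures for ZYPREXA im. Medication use and discontinuation, whether from any cause or because of an adverse event, are given the same window there. The analysis sections use other windows:

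- Section 7.2 reports adverse events for "period 1 + 2 (from the administration timepoint of Zyprexa IM until and not including the administration timepoint of Olanzapine extended-release formulation"), plus an overall summary after the first dose of IMP, which is longer still.
- Section 7.6.1 reports failure to complete "separately for period 1+2 up until the Olanzapine extended-release formulation administration".
- Section 7.11 reports medication "for period 1 and period 2 (day 4 up until day R1").
- Section 5.2 counts "patients who discontinue the trial prior to TV44749 formulation administration", with no starting point at the im dose.

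In period 2, SAP Section 2.1 says, "participants will resume treatment with the allowed antipsychotic treatments and discontinue 24 h prior to sc injection on day R1". Protocol Table 2 marks that resumption from the day 5 visit.

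**QTcF.** Section 1.4 defines the period 3 measure as a change from baseline of ≥30 and ≥60 msec. Section 7.10 counts >30 and >60, including in its separate period 3 presentation.

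**Day R29.** Section 7.11 runs period 3 to R29 and starts follow-up on R29. Sections 5.2, 7.2 and 7.6.1 start follow-up on R30. Footnote a of Section 1.1 closes period 3 with those R29 assessments that are done before the participant goes back on antipsychotics. The 28-day adverse-event measures and the period 3 concomitant-medication measure both carry that footnote. Protocol Table 5 schedules the antipsychotic restart at the R29 visit (window ±1 day), and its footnote b requires that visit's assessments to come first.

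**The concern.** A programmer who follows Section 7 literally would produce tables that differ from the measures in Section 1. The period 1+2 tables cannot stand in for the 24-hour measures. Most of that window is time in which another antipsychotic may be taken, so adverse events are no longer attributable to an im-only interval, and the medication table will record planned background treatment.

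At R29 the risk is similar. By the dates in Section 7.11, a restart made as planned at the end of period 3 can be reported as medication used during period 3. Protocol Section 6.8.2 allows the same five antipsychotics as additional rescue, so by drug name a planned restart could be read as rescue during sc treatment. The QTcF difference means that an endpoint and its table use different rules.

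The SAP states that it prevails over the protocol where they differ, so a conflict inside the SAP has no document above it to settle it. It would be settled by undocumented choices, possibly after the data have been seen.

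**Working it through.** The trial is descriptive, with no sample size calculation, so the check is a comparison of text plus arithmetic on the windows.

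**(a) Length of the period 1+2 window**

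Inputs: the im dose is on day 4. Without an extension R1 is day 13. With the maximum extension, day 12 counts as extension day 1 and R1 is extension day 7, which is day 18 (SAP Section 2.1).

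Formula: hours = (R1 day − 4) × 24.

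- No extension: (13 − 4) × 24 = 216 h. This reproduces the plan's own figure: the 216 h PK sample is drawn just before sc dosing in participants who go straight to period 3.
- Maximum extension: (18 − 4) × 24 = 336 h.

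| | No extension | Maximum extension |
|---|---|---|
| Period 1+2 window | 216 h | 336 h |
| Ratio to 24 h | 216/24 = 9 | 336/24 = 14 |
| Outside the 24 h measure | 192/216 = 89% | 312/336 = 93% |
| Other antipsychotics allowed (less the first and last 24 h) | 168/216 = 78% | 288/336 = 86% |

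The last row assumes that resumption starts exactly 24 h after the im dose. Protocol Table 2 gives only the day, so those figures are approximate. Participants who leave before R1 have shorter windows.

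If only dates are available, a dose at clock hour T on day 4 followed to the end of day 5 spans 48 − T hours, which is more than 24 and less than 48. The Protocol requires onset and end dates for adverse events (Section 8.4.4) and start and end dates for medication (Section 6.8). It does not say that clock times are recorded for them.

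**(b) QTcF**

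A change of exactly 30 or 60 msec meets ≥ but not >; no other value is affected. As an illustration only, take whole-millisecond, normally distributed changes with an assumed mean of 0 to 10 msec and an assumed SD of 10 to 20 msec. The chance of exactly 30 msec is then 0.04% to 1.2% per reading, which is 7% to 28% of the readings that meet ≥30. Section 7.10 prints ≥25% for PR and QRS in the same list, so the strict sign for QTcF does not look like a PDF reading error.

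**(c) R29**

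| Source | End of period 3 | Start of follow-up |
|---|---|---|
| SAP 1.1, footnote a | R29 assessments made before the antipsychotic restart | not stated; by implication after them |
| SAP 2.1 and 4.4, design text | R29 | R29 |
| SAP 7.11 | R29 | R29 |
| SAP 5.2, 7.2, 7.6.1 | R29 | R30 |

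Take a restart on R29, after the visit assessments. Footnote a puts it outside period 3. The dates in Section 7.11 put it in both periods. A pure R29/R30 calendar split would put it in period 3 only. Because of the ±1 day window, a restart at a visit held on R28 also falls in period 3 by calendar date. None of the four analysis sections states the footnote's rule.

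**The case against.** Several points on the other side stand.

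- A reader might infer that the plan gives no output at all for the 24-hour im measures. That goes too far. Section 5.2 counts both the safety analysis set (at least one IMP dose, Section 3.3) and the patients who continued to period 2. Because the im dose comes first and period 2 starts on day 5, the difference gives any-cause loss between the im dose and day 5. It gives no reason for the loss, and nothing on adverse events or medication. Laboratory, vital-sign, ECG and local-tolerability results are summarised by visit or time point and are not part of this gap.
- The 24-hour measure is itself labelled day 4 to day 5, and resumption is marked at the day 5 visit. A date-based version therefore has some overlap with other antipsychotics too. This is why the fix shows those separately.
- For QTcF, Section 7.10 does provide a separate period 3 count, so only the cut-off is at issue. The corresponding protocol row is not legible in the public text, so the sponsor's intended sign cannot be confirmed there.
- Footnote a is already worded as an analysis rule. It splits R29 within the day, so a follow-up that begins on R29 is consistent with it. A reader might take R30 as the correct start and Section 7.11 as the only error, but the documents do not support that: an R30 start in Section 7.11 would place a planned R29 restart wholly in period 3.

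What remains is that Section 7 never applies the footnote, and its sections disagree with one another.

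**Conclusion.** The concern holds as a minor one. All three mismatches are plain in the SAP text.

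- **24-hour im measures:** no 24-hour summary is specified for adverse events, concomitant medication or discontinuation due to an adverse event. The planned window is nominally 9 to 14 times as long for participants who reach R1.
- **QTcF:** the measure and its table differ only at changes of exactly 30 or 60 msec.
- **R29:** every participant who restarts an antipsychotic at the R29 visit may be affected. That number is not known from the documents. It might be equated with the approximately 60 planned completers, but completers are defined by R84, and people who leave after R29 can also restart at that visit.

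Nor does any of this reach the primary result. These are descriptive safety tables in an open-label trial with no inferential testing, and the primary PK measures are unaffected. The window lengths rest on nominal study days, and the QTcF percentages on assumed distributions.

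**What to change.** **(a)** In Sections 7.2, 7.6.1/5.2 and 7.11, keep the period 1+2 tables and add im summaries for the 24 h after dosing: adverse events, concomitant medication, discontinuation for any reason, and discontinuation due to an adverse event. If only dates exist, use day 4 post-dose to day 5, state that this can exceed 24 h (up to nearly 48 h), and show antipsychotics resumed on day 5 separately.

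**(b)** Use one QTcF cut-off in Sections 1.4 and 7.10. The default for the period 3 count should be the endpoint definition in Section 1.4 (≥30 and ≥60 msec).

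**(c)** Apply footnote a as the single rule in Sections 5.2, 7.2, 7.6.1 and 7.11:

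- antipsychotics restarted after the R29-visit assessments, whichever day in the ±1 day window that visit falls on, count in follow-up only;
- adverse events dated R29 without a clock time default to period 3;
- if the visit is missed, use the R29/R30 calendar split.

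The cost is SAP wording and a few table shells. The dates are already collected; an exact 24-hour cut may not be possible unless clock times are recorded. No change to trial conduct is needed.

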8.4.4. Recording of Adverse Events and Serious Adverse Events

All AEs that occur during the defined trial period must be recorded both on the source documentation and the CRF, regardless of the severity of the event or judged relationship to the IMP. The Investigator will record all relevant information regarding every AE/SAE and will categorize each as guided in Figure 2. For SAEs and PDAESI for expedited reporting to Global PV, the Serious Adverse Event and PDAESI Form must be completed and the SAE and the PDAESI must be reported within 24 hours (Section 8.4.6 and Section 8.4.7). The Investigator does not need to actively monitor participants for new AEs after the end of the trial.

SAEs occurring in a participant after the EOT should be reported to the Sponsor if the Investigator becomes aware of them, following the procedures described in Section 8.4.7.

The onset and end dates, duration (in case of AE duration of less than 24 hours), action taken regarding IMP, treatment administered, and outcome for each AE must be recorded both on the source documentation and the CRF.

The relationship of each AE to IMP (and relationship to the device, if applicable), and the severity and seriousness of each AE, as judged by the Investigator, must be recorded.

Figure 2: Decision Tree for Adverse Events and Adverse Device Effects Classification

AE=adverse event; ADE=adverse device effect; CIOMS=Council for International Organizations of Medical Sciences; CRF=case report form; IEC=Independent Ethics Committee; IRB=Institutional Review Board; SADE=serious adverse device effect; SAE=serious adverse event.

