8.7. Pharmacokinetics

8.7.1. Timing of Pharmacokinetic Sampling

Blood samples (3 mL) will be obtained via direct venipuncture or indwelling catheter for the determination of plasma concentration of olanzapine and potentially for olanzapine metabolites at the time points detailed in [Table 1](#) to [Table 5](#).

Specimen collection, processing, and handling requirements are detailed in the Laboratory Manual.

Every effort must be made to obtain the PK samples within the allowed limits for sampling times, as defined in [Table 6](#) and [Table 7](#). The exact time of sample collection must be noted in the source documents and CRF.

When the PK blood sample collection coincides with safety assessments, PK blood samples should be collected as close to the scheduled time point as possible. Assessment of vital signs and ECGs should precede PK blood sampling.

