9.2.2. Handling of Missing Data

For all variables, only the observed data from the participants will be used in the statistical analyses, unless otherwise specified.

In general, missing data will not be imputed. Partial or missing dates of AEs and concomitant medications may be imputed and detailed in the SAP. Other specific imputations for missing safety features at baseline will also be detailed in the SAP.

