4.3. Handling Withdrawals and Missing Data

Missing data will not be imputed. In general, for all variables only the observed data from the patients will be used in the statistical analyses.

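### SAP 7.2 closes period 1+2 at the sc injection but opens period 3 on calendar day R1, and no rule places adverse events whose order relative to dosing is unknown

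*SAP*

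**What the plan says.** SAP 7.2 divides the adverse event summaries, and again the summaries of protocol-defined events of special interest, into three periods.

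- Period 1+2 is bounded by dosing: "from the administration timepoint of Zyprexa IM until and not including the administration timepoint of Olanzapine extended-release formulation".
- The later periods are bounded by days: "for period 3 (day R1 to day R29) and for the follow up period (day R30 to day R84").
- A washout listing also ends at a dose: "Wash-Out period (from day 1 to the administration of Zyprexa im").

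The secondary safety endpoints (SAP 1.1, protocol 3.1) are the number and percentage of participants with at least one TEAE, or at least one SAE, over the 28 days after the sc injection, with R1 to R29 in brackets. SAP 1.1 footnote a settles how R29 is handled but starts period 3 simply at day R1.

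For timing, protocol 8.4.4 requires these items for each event: "The onset and end dates, duration (in case of AE duration of less than 24 hours), action taken regarding IMP, treatment administered, and outcome". An onset time is not listed. On missing data, protocol 9.2.2 says "Partial or missing dates of AEs and concomitant medications may be imputed and detailed in the SAP", while SAP 4.3 says "Missing data will not be imputed" and names no exception. The SAP's introduction gives the SAP precedence where the two documents differ.

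**The concern.** Two windows meant to adjoin use different kinds of boundary. Between the start of R1 and the sc injection both definitions apply, so a pre-dose R1 event is tabulated twice and is attributed to a formulation the participant had not yet received.

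Such events are foreseeable. The R1 ECG, vital signs with orthostatic measurements, physical examination and laboratory samples are all scheduled before dosing (protocol Tables 3 and 4), and clinically significant findings from them are to be recorded as adverse events (protocol 8.3). Protocol 4.1 also has the oral antipsychotic stopped 24 hours before the injection.

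At stake are the secondary safety counts by formulation, which are read descriptively in small cohorts. There is a second gap: when the order of onset and dosing is not known, or the onset date is incomplete, no written rule says which period the event belongs to.

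**Working it through.** The plan states no figure to reproduce: both documents say that no formal sample size calculation was done, and no event rate is given. The check is a comparison of texts, followed by one line of arithmetic for scale.

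**1. Take an event that starts on R1 before the sc injection.**

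- Period 1+2 (SAP 7.2): it starts after the im dose and before the sc administration timepoint, so it is in.
- Period 3 (SAP 7.2, footnote a): its onset day is R1, so it is in.
- TEAE status (protocol 8.4.2): treatment emergence runs from the first dose of any IMP, normally ZYPREXA im on day 4. The event is already a TEAE, so this definition does not screen it out.
- Secondary endpoint (SAP 1.1): the bracketed days include it, while the wording about the period after the injection excludes it. The endpoint text disagrees with itself for this event.

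**2. Compare with the rest of the SAP.** SAP 4.2 takes R1 pre-dose assessments as the sc baseline. SAP 4.4 maps an early termination on R1 before dosing to the earlier period. SAP 7.6.1 ends period 1+2 at the sc administration. All three point to the dose as the intended boundary; the period 3 wording in SAP 7.2 does not say so.

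**3. Ask whether the required data could apply a dose-time split.** Protocol 8.4.4 requires dates, plus a duration for events shorter than 24 hours. A duration does not show whether onset came before or after the injection. For PK samples, by contrast, protocol 8.7.1 is explicit: "The exact time of sample collection must be noted in the source documents and CRF". No equivalent sentence covers adverse events.

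**4. Ask where an event of unknown order goes.** Protocol 9.2.2 sends partial event dates to the SAP; SAP 4.3 gives only the general bar on imputation. SAP 7.2 has a default for missing causality (counted as related) but none for missing or partial dates.

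**5. Scale.** If k participants have their only period 3 event reallocated in a cohort of n, the percentage moves by 100 × k / n.

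- n = 20 (planned completers per cohort), k = 1: 100 × 1/20 = 5.0 points; k = 2: 10.0 points.
- n = 60 (all cohorts), k = 1: 100 × 1/60 = 1.7 points.

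The 20 is a completer target. The safety denominator is participants dosed and may be larger. As an extreme assumption, if all 95 planned enrolments were dosed and split equally over three formulations, one participant would move the figure by 100 × 3/95 = 3.2 points.

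**The case against.** The best reply is that the intent is clear. The endpoint covers time after the sc injection, and the baseline, early-termination and tolerability rules all use the dose as the dividing line, so the R1 in period 3 is shorthand. That stands as a reading of intent, and it is why the repair is small. It does not remove the literal overlap: a programmer following SAP 7.2 and footnote a would count the event twice.

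Several stronger inferences are tempting but not supported:

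- *That only onset dates are collected, so the split cannot be applied.* Protocol 8.4.4 lists required items and does not exclude a time; it also asks for all relevant information on each event. The CRF may already have a time field.
- *That partly dated events drop out of the secondary endpoints.* Neither document says so. SAP 4.3 uses observed data, and known date parts may place an event in one window. Inpatient stays, frequent visits and data queries also make an unplaceable date in period 3 less likely.
- *That day 4 ambiguity affects the secondary endpoints.* It reaches only the washout listing, the period 1+2 summary and the exploratory 24-hour ZYPREXA endpoint.
- *That the SAP breaks a protocol commitment.* Protocol 9.2.2 is permissive, so this is a gap.
- *That every misplaced event costs 5 points.* The endpoint counts participants with at least one event, so only a participant's sole period 3 event matters.

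It is also fair to object that a default of counting unknown-order events as post-dose could charge pre-dose events to the depot. That is a reason to make it a last resort, after all recorded information has been used.

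**Conclusion.** The point holds as a mismatch of boundaries in SAP 7.2 and footnote a, together with a missing allocation rule. As written, a pre-dose R1 event counts in both periods and in the secondary TEAE or SAE figure for the sc product. This follows from the text alone and remains even if the CRF records onset times.

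The missing rule matters only for events whose order relative to dosing cannot be settled from the recorded data. How many there will be, and how many pre-dose R1 events, the documents do not say. The size is therefore conditional: about 5 points of a cohort percentage per participant whose only period 3 event is affected, assuming about 20 in the cohort, and less if more are dosed. No formal safety testing is planned, so the consequence is a distorted descriptive rate, not a wrong test result. It should be corrected before database lock.

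**What to change.** 1. **SAP 7.2 and footnote a.** Start period 3 at the sc administration timepoint, for both the adverse event and the special-interest summaries, and state that each event belongs to one period only. Leave the R29 end of footnote a as it is.
2. **SAP 4.3 and 7.2.** Add an exception to the no-imputation rule for adverse event dates. Use the known date parts, the end date and any recorded time or pre-/post-dose information first. Only if these cannot establish the order relative to dosing, count the event as after dosing, in one period.
3. **Data collection.** Where the CRF does not already do so, record an onset time or a pre-/post-dose flag for events starting on a dosing day. Do this prospectively: six participants were already in cohort 1A by 3 May 2024, and clock times for past events may not be recoverable.

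The cost is a few SAP sentences, which SAP 2.5.2 allows by amendment before lock, and possibly one CRF field. The default in item 2 may slightly raise the reported period 3 TEAE rates; that is consistent with how SAP 7.2 already treats missing causality.
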